5
6
7
8
9

STUDY PROTOCOL: GENETIC EPIDEMIOLOGY OF CHRONIC OBSTRUCTIVE PULMONARY DISEASE (COPDGene®)

10 **I. BACKGROUND AND SIGNIFICANCE**

11 Chronic obstructive pulmonary disease (COPD) is the third leading cause of mortality in the
12 United States (1). COPD is a heterogeneous syndrome, with varying contributions of emphysema
13 and airway disease in each COPD subject. Genetic studies of complex diseases like COPD have
14 the potential to provide insight into the pathophysiological mechanisms of COPD susceptibility
15 and heterogeneity. A strong genetic basis for the susceptibility of smokers to develop COPD is
16 suggested by:

- 17 (1) Marked variability in the development of airflow obstruction among smokers (2)
18 (2) Clear familial clustering of COPD and COPD-related phenotypes (3) and
19 (3) Evidence of linkage for COPD-related phenotypes to specific genomic regions in families
20 with severe, early-onset COPD (4).

21
22 COPD is a heterogeneous condition with variation in rates of disease progression, symptoms and
23 CT characteristics. We have previously identified CT subtypes of disease based on visual
24 scoring and found variation in progression of disease based on spirometry and CT metrics
25 (emphysema, airway disease).

26 Case-control studies have been performed for many candidate genes in COPD, but the results
27 have been inconsistent (5). Recent progress in single nucleotide polymorphism (SNP)
28 genotyping and DNA sequencing allows for association studies on a genome-wide scale;
29 however, the multiple statistical tests involved in genome-wide association (GWA) studies of
30 hundreds of thousands of SNPs raise challenges in separating true from false positive
31 associations (6). In addition, genetic association studies within a single racial/ethnic group may
32 not generalize to other populations.

33 To address the multiple testing and generalizability problems of GWA studies, we propose to
34 perform a comprehensive GWA and DNA sequencing study to identify genes influencing COPD
35 in two major racial/ethnic groups (non-Hispanic Whites and African Americans). Our primary
36 hypotheses are:

- 37 (1) Precise characterization of COPD subjects using computed tomography – as well as
38 clinical and physiological measures assessed longitudinally – will provide insight that will
39 enable the broad COPD syndrome to be decomposed into clinically significant subtypes.

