671 trapping, six minute walk distance (6MWD), and health-related quality of life. Longitudinal
672 analyses will be performed with quantitative imaging phenotypes from the Phase 1, 2, and 3
673 visits. Key predictor variables to be assessed for these outcomes include age, gender, current
674 smoking status (at each visit), pack-years, baseline lung function, baseline CT emphysema and
675 airway measures, respiratory symptoms (e.g., chronic bronchitis, dyspnea), respiratory
676 medications, and co-morbid illnesses (including lung cancer and coronary artery disease).
677 Exacerbation frequency will be assessed as a predictor of primary outcome measures.
678 Transformations of CT and spirometric progression measures from among the Box-Cox family
679 of transformations will be considered to stabilize variance estimates across the ranges of CT
680 measurement values. We will compare the demographic and clinical characteristics of subjects
681 who have follow-up data to those subjects missing due to death and those subjects missing due to

682 loss to follow-up. Longitudinal analysis will be performed including time-dependent covariates
 683 such as change in current smoking status. Time-dependent covariates in these analyses include
 684 change in current smoking status and change in pulmonary medications. Disease progression and
 685 mortality will be simultaneously assessed to limit potential bias introduced by differential
 686 survival. This analytical approach considers the joint distribution of the vector of repeated
 687 measures (i.e., longitudinal progression of PFT abnormalities and CT measures) simultaneously
 688 with time to event (i.e., mortality) using the method developed by Hogan and Laird(10).
 689 The power to detect differences in 10-year changes between subtypes of COPDGen subjects
 690 was assessed for FEV₁, PERC15, adjusted lung density, and % gas trapping. These calculations
 691 used the mean and standard deviation (SD) with estimated changes in FEV₁(11), PERC15(12),
 692 adjusted lung density, and % gas trapping based on the 5-year follow-up visits. We assumed a
 693 significance level of 0.05 and equal variance of the change in each subtype group. These
 694 conservative calculations are based on comparing differences in rates of change for COPD-
 695 related phenotypes among two hypothetical groups of subjects ranging in size from 250 to 2000,

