 696 which will be created from the 4500 subjects with follow-up spirometry, clinical measures, and
 697 chest CT scans in Phase 3 (**Table 2**). Using these assumptions, there is adequate power to detect
 698 differences between subtype groups with as few as 250 subjects. By 2-sided log rank test, we
 699 will have virtually 100% power to detect a 15% difference in all-cause or cause-specific
 700 mortality between the slow and fast FEV₁ decline groups in Table 2.
 701

Table 2: Power (%) for Longitudinal Epidemiology Analysis

Outcome	Difference Between Groups over 10 yrs	Sample Size of Each Subtype Group for Pairwise Comparisons			
		250	500	1000	2000
FEV ₁ , ml	100	97	100	100	100
	200	100	100	100	100
PERC15	4	75	96	100	100
	8	100	100	100	100
Adjusted Lung Density	2	46	75	96	100
	4	96	100	100	100
% Gas trapping	2	70	94	100	100
	3	96	100	100	100

702
 703 The primary phenotypes for genetic, transcriptomic, and proteomic analysis will be each COPD
 704 subtype vs. smoking controls; the quantitative emphysema and airway disease axes; and the
 705 change in FEV₁ and adjusted lung density between the 5-year and 10-year visits. In addition, a
 706 number of secondary analyses will be performed, including: a) presence/absence of COPD
 707 (comparing subjects with GOLD 2-4 COPD to smoking controls); b) cross-sectional measures of
 708 CT emphysema, CT gas trapping, CT airway wall area, FEV₁, 6MWD, oxygen saturation,
 709 emphysema distribution, and chronic bronchitis; and c) longitudinal measures of exacerbation
 710 frequency and change in CT gas trapping, CT airway wall area, and 6MWD. Cross-sectional and
 711 longitudinal COPD-related phenotypes will be assessed within each COPD subtype and within
 712 the entire study population. Longitudinal imaging and lung function phenotypes will be assessed
 713 as both change over time (between the 5 and 10-year visits and across all three visits) and
 714 average outcomes over all three visits.
 715

716 Phase 2 blood RNA-Seq will be used to generate gene, exon, and isoform-level estimates of
 717 relative expression abundance. RNA-Seq data will be processed by the CDNM bioinformatics
 718 pipeline that addresses sequencing errors and other technical artifacts. Alignment to the human

719 reference genome will be performed with STAR(13), followed by multiple quantification and
720 analysis options, including DESeq2(14), DEXSeq(15), and voom/limma(16). While isoform-

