Appendix B- Phase 2 (Year 5 and Year 1 for New Nonsmokers)- Completed

I. COPDGene Phase 2 Return Visit

In addition to the cross-sectional subject data collected in the baseline COPDGene study visit, disease progression and incidence of COPD in smokers are important additional endpoints for genetic association studies. We have completed enrollment of 10,300 subjects as the first phase of this project and now propose to invite these subjects to return for a second evaluation five years after their initial visit to assess disease incidence and/or progression in COPDGene subjects.

The primary goals of COPDGene Phase 2 are: 1) to identify new genetic loci that influence the development and/or progression of chronic obstructive pulmonary disease (COPD) and COPD-related phenotypes, and 2) to reclassify COPD into subtypes that can ultimately be used to develop effective subtype-specific therapies and prevention. The reclassification of COPD will be done using imaging, clinical and physiologic characteristics, longitudinal progression, long-term outcomes, and genetics.

In addition to identifying COPD genetic determinants, this program will characterize the natural history of COPD and identify well-characterized COPD subtypes. Improved understanding of COPD subtypes and genes controlling susceptibility to COPD could lead to novel pathophysiological insights, refined diagnostic criteria, and new treatment approaches. Moreover, the availability of comprehensive genetic data and longitudinal data on a large biracial group of smokers will be an invaluable national resource for other investigators.

New Non-Smoker Controls

To reach our Phase 1 goal of up to 12,000 subjects, we plan to enroll up to an additional 1,500 subjects in Phase 2. We will target enrollment of additional non-smokers without lung disease in Phase 2 of COPDGene. By providing insight into the normal effects of aging in healthy subjects, these subjects will allow us to correctly interpret the chest CT scans, lung function, health status and other features of our current cohort. For example, aging is associated with loss of lung elasticity, a characteristic feature of emphysema. Without knowledge of the effects of age, gender and race on the lungs of healthy subjects, we cannot accurately determine whether CT scans of subjects with a smoking history are normal or abnormal, or assess disease severity.

II. SUBJECT SELECTION – Phase 2

Return Visit

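### Where a subtype or decline group is assigned from Phase 1-to-2 change, a difference in 10-year change does not confirm prognosis, and the protocol does not separate assigning data from confirming data

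*Protocol*

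**What the plan says.** **How subtypes are formed.** Appendix B, section I, states the Phase 2 goal of reclassifying COPD into subtypes and says this will be "done using imaging, clinical and physiologic characteristics, longitudinal progression, long-term" outcomes and genetics. That appendix is headed "Appendix B- Phase 2 (Year 5 and Year 1 for New Nonsmokers)- Completed". In the current text, hypothesis 1 of Section I expects CT together with "clinical and physiological measures assessed longitudinally" to allow COPD to be split into subtypes. No assignment rule for the Phase 3 subtypes is printed.

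**What is then compared.** Section VII introduces Table 2 with "The power to detect differences in 10-year changes between subtypes of COPDGen subjects". The groups are hypothetical, of 250 to 2,000 subjects each, drawn from the 4,500 with Phase 3 follow-up. The next sentences call them groups of slow and fast FEV1 decline and claim near-certain log-rank power for a 15% mortality difference between them. Later in Section VII: "The primary phenotypes for genetic, transcriptomic, and proteomic analysis will be each COPD" subtype against smoking controls. Longitudinal phenotypes are to be assessed both between years 5 and 10 and across all three visits.

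**Purpose.** Aim 1 is to confirm prognostication of clinical progression in an estimated 6,500 subjects: 4,500 who return at year 10 and 2,000 who die before that visit.

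**The concern.** Confirming a prognosis requires an outcome that did not help to form the group. Ten-year change is the sum of the change from Phase 1 to Phase 2 and the change from Phase 2 to Phase 3. If the first part enters the assignment, the groups differ on the sum even when the subtype says nothing about what follows year 5.

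Two related overlaps follow from the same passages:

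- Groups created from subjects with Phase 3 follow-up consist of people who survived to about year 10. Deaths before that visit cannot be counted in a log-rank test between them.
- If genotype entered a subtype definition, as the Phase 2 goal allows, testing that subtype against genotype would be circular.

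At stake is whether Aim 1 could report a confirmed prognostic subtype that has no predictive value beyond the decline already seen.

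**Working it through.** **Step 1. Reproduce Table 2.** The SDs are not printed. Taking a two-sided 0.05 test with equal groups, the FEV1 cell (100 ml, 250 per group, 97%) gives

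SD = 100 / [(1.960 + 1.881) × √(2/250)] = 100 / (3.841 × 0.0894) = 291 ml.

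The same back-solving gives 17.0 for PERC15, 12.0 for adjusted lung density and 9.0 for gas trapping. With these, all 32 cells reproduce to within 2 points. The power table is internally consistent, so the point does not rest on an arithmetic error.

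**Step 2. Model.** Let V1, V2 and V3 be FEV1 at the three visits. Assumptions:

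- true changes in the two intervals are independent with equal variance;
- each visit carries error SD s, varied from 0 to 150 ml;
- the assignment score has correlation ρ with V2 − V1 and no relation to decline after year 5;
- groups are a median split of the score.

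With the SD of V3 − V1 fixed at 291:

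- covariance of V2 − V1 with V3 − V1 = 291²/2 = 42,340, whatever s is;
- SD of V2 − V1 = √(42,340 + s²);
- expected group difference in 10-year change: d = 2√(2/π) × ρ × 42,340 / √(42,340 + s²), where 2√(2/π) = 1.596;
- standard error = √(291² − d²/4) × √(2/n).

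**Step 3. Results at 250 per group.**

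| Error SD s (ml) | ρ | d (ml) | d / SE | Rejection at 0.05 |
|---|---|---|---|---|
| 0 | 0.1 | 32.8 | 1.26 | 24% |
| 100 | 0.1 | 29.5 | 1.14 | 21% |
| 150 | 0.1 | 26.5 | 1.02 | 18% |
| 0 | 0.3 | 98.5 | 3.84 | 97% |
| 100 | 0.3 | 88.6 | 3.44 | 93% |
| 150 | 0.3 | 79.6 | 3.09 | 87% |

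For example, with s = 0 and ρ = 0.3: d = 1.596 × 0.3 × 42,340 / 205.8 = 98.5 ml, against the 100 ml difference planned in Table 2. At ρ = 0 a simulation rejected 5.6% of the time. At 1,000 per group, ρ = 0.1 gives about 53% to 72% and ρ = 0.3 gives 100%.

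**Step 4. What the difference consists of.** The part of the covariance due to true early change is 42,340 − s². As a share this is 100% at s = 0, 36,715/42,340 = 87% at s = 75, and 19,840/42,340 = 47% at s = 150. Much of the difference is therefore real decline before year 5. It is an error only if read as prediction of later decline.

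**Step 5. Check the remedy.** In simulation (2,000 replicates, 250 per group; s = 75, 100, 150; ρ = 0.1, 0.3, 1), regressing V3 on V1, V2 and group rejected 4.6% to 5.6% of the time. The unadjusted 10-year test rejected 18% to 100% in the same runs.

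**The case against.** The strongest reply is that the protocol never joins the two texts. The construction sentence is a goal of a completed phase, and Section VII does not adopt it. Section I also mentions CT subtypes from visual scoring, with progression as the outcome; if those are assigned at baseline, the overlap disappears. Table 2 uses hypothetical groups, and ρ is assumed. Subtype algorithms are commonly left to an analysis plan. All of this stands, and it makes the point conditional. What remains is that the protocol itself states both the ingredients and the outcome interval, describes its own Table 2 groups by a rate of decline, and sets a confirmatory aim.

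A reader might infer more than the documents support:

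- *Subtypes built on long-term outcomes are tested on mortality.* Not stated. Mortality power is given for FEV1-decline groups, and decline and death are different variables. The narrower problem is that these groups are drawn from subjects seen at Phase 3.
- *The 5-to-10-year genetic analysis is biased in the opposite direction through the shared Phase 2 reading.* That change is a phenotype for genetic, transcriptomic and proteomic analysis, and no between-subtype test of it is stated. Germline genotype does not share spirometry error.
- *The subtype genetic results are circular.* Only if genotype enters the definition, which no current Phase 3 passage says.
- *Every high-risk comparison is affected.* The Short-Term Follow-Up selects subjects from Phase 2 data and observes them about a year after Phase 3, so it is already largely separated in time.

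The planned joint model of progression and survival addresses differential survival. It does not remove the overlap between assignment and outcome.

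**Conclusion.** The point holds conditionally. For any subtype or decline group whose assignment uses Phase 1-to-2 change of the measure being tested, a significant 10-year difference is not evidence of prognosis. At 250 per group the test rejects about 20% of the time at a correlation of 0.1 and about 87% to 97% at 0.3, with no group effect after year 5. These figures rest on the SD implied by Table 2 and on assumed values for the correlation, the visit error and independence of the two intervals. The documents give none of these, so the figures show the mechanism and its possible size; they do not estimate what will happen.

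For mortality, the wording needs a time origin, because groups formed among Phase 3 attendees can contribute only later deaths. For genetics, the need is to state that genotype is not an ingredient of the subtype.

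**What to change.** Add to Section VII a rule that data used to assign a subtype or decline group may not be part of the outcome used to confirm it:

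1. If assignment uses Phase 1 data only, 10-year change may be tested.
2. If assignment uses Phase 1-to-2 change, test the Phase 3 value with both the Phase 1 and Phase 2 values of that measure as covariates, or use Phase 3a-to-3b change. Label the 10-year difference descriptive.
3. For mortality by FEV1-decline group, define the group at a stated visit, include everyone then alive, and count only later deaths. The continuing follow-up in Section VI supplies these.
4. For genetic association, use subtype definitions that exclude genotype.

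Also state whether the Phase 3 subtypes are the Phase 2 classification. If they come from baseline data without genotype, one sentence settles the matter for the subtypes.

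The cost is wording only, with no new data. The differences will be smaller and the apparent power lower than in Table 2, some subtype versions will lose inputs, and the Phase 3a-to-3b option is limited to the roughly 800 Short-Term Follow-Up subjects.
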